9. Female patient must be postmenopausal (no menses for ≥ 12 consecutive months) or surgically sterile (ie, bilateral oophorectomy, hysterectomy, or tubal sterilization [tie, clip, band, or burn]); must agree to completely abstain from heterosexual intercourse; or, if heterosexually active, must agree to use 1 of the following methods of birth control from the date she signs the informed consent form (ICF) until 90 days after the final dose of study drug:

- Progesterone implant and/or an intrauterine device (IUD)
- Combination of 2 highly effective birth control methods (eg, diaphragm with spermicide plus a condom, condom with spermicide plus a diaphragm or cervical cap, hormonal contraceptive [eg, oral and transdermal patch] plus a barrier method, or partner with vasectomy [conducted ≥ 60 days before the Screening Visit or confirmed via sperm analysis] plus a hormone or barrier method).

10. Male patient must be surgically sterile by vasectomy (conducted ≥ 60 days before the Screening Visit or confirmed via sperm analysis), must agree to completely abstain from heterosexual intercourse, or, if heterosexually active, must agree to use a combination of 2 highly effective birth control methods (eg, partner use of progesterone implant and/or IUD, condom with spermicide plus a partner diaphragm or cervical cap, partner hormonal contraceptive [including progesterone implant] plus a barrier method, or postmenopausal partner [for ≥ 1 year] plus barrier method) from the Screening Visit through 90 days after the final dose of study drug.

11. Patient is fluent in the language of the local ICF (eg, English, Spanish, Arabic, French).

12. Patient completes daily eDiary entries for at least 10 days during the last 14 days of the Run-in Period as assessed at the Randomization Visit. (Note: To enter the Run-in Period, patient must meet all eligibility criteria applicable to the Screening Visit.)

EXCLUSION CRITERIA

Patients who meet any of the following criteria will not be eligible to participate in the study:

1. Patient requires a program of prescheduled, regularly administered chronic blood transfusion therapy, has received a transfusion in the 8 weeks before the Randomization Visit, and/or is scheduled to receive a transfusion during the study.
2. Patient has been hospitalized for an SCD-related complication in the 4 weeks before the Randomization Visit.

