- Run-in Period:** The single-blind Run-in will begin at least 3 days after the Screening Visit and is defined as the 14 to 17 days before the first dose of double-blind study drug on Day 1. At the Run-in Visit, eligible patients will take their first single-blind (placebo) dose in the clinic, will undergo safety and pharmacodynamic (PD) assessments, and will complete patient-reported outcome (PRO) questionnaires in an eDiary (a handheld personal electronic device) that will be issued for their use. They will continue to take once-daily single-blind placebo at home and will record daily and weekly assessments in their eDiary throughout this period. Patients will be required to complete at least 10 days of daily assessments during the final 14 days of the Run-in Period to remain eligible for randomization into the Treatment Period.

Treatment Period: The double-blind Treatment Period will begin on Day 1 at Randomization (there is no Day 0) and will end after the End-of-Treatment (EOT) Visit on Day 85 (-7/+4).

Eligible patients will take their first dose of double-blind study drug in the clinic on Day 1 and will undergo safety, PRO, PK, and PD assessments at prespecified times according to the [Schedule of Events](#). Patients must remain in the clinic at least 6 hours postdose and thereafter will be allowed to leave at the Investigator's discretion. Starting on Day 2, patients will take their daily double-blind study drug dose at home, per Section [3.5.4.1](#). Also on Day 2, preferably in the afternoon, patients will receive a phone call for adverse event (AE) and concomitant medication and procedure(s) assessment. Throughout the Treatment Period, patients will continue to record daily assessments in their eDiary.

At their Week 1 (Day 8 [± 1]) and Week 4 (Day 29 [± 3]) visits, respectively, patients who meet the uptitration criteria (see Section [3.5.4.2](#)) will begin taking the applicable higher dose. At these visits, patients must again stay in the clinic at least 6 hours postdose to undergo safety, PRO, PK, and PD assessments at prespecified times according to the [Schedule of Events](#) and thereafter will be allowed to leave at the Investigator's discretion. On the day after these 3 visits, preferably in the afternoon, patients will receive a phone call for assessment of AEs and concomitant medication(s) and procedure(s).

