During Week 2, Week 3, Week 4, Week 6, and Week 10, patients will receive a phone call for AE and concomitant medication and procedure(s) assessments.

At Week 12 (EOT Visit), patients will return to the clinic for safety, PRO, PK, and PD assessments and will return their eDiary and any unused study drug.

Follow-up Period: The Follow-up Period will begin immediately after the EOT Visit and will last for 28 (-3/+7) days. On Day 113 (-3/+7), patients will return to the clinic for the Follow-up Visit and final safety, PRO, PK, and PD assessments.

The study schematic ([Figure 1](#)) shows all study visits and calls. For a detailed schedule of all study visits and assessments, refer to the [Schedule of Events](#).

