## 8.4. Patient-reported Outcomes

### 8.4.1. Sickle Cell Disease – Symptom Assessment Form (SCD-SAF)

#### 8.4.1.1. Primary Analysis of SCD-SAF

The SCD-SAF endpoints are listed here:

- Changes from baseline in SCD-SAF total score at Weeks 4, 8, 12, and EOT
- Pain as measured on the 11-point numerical rating scale (NRS) by week and for the overall Treatment Period
- Percent change from baseline in pain as measured on the 11-point NRS by week and for the overall Treatment Period
- Change from baseline in pain as measured on the 11-point NRS by week and for the overall Treatment Period
- Change from baseline in fatigue as measured on the 11-point NRS by week and for the overall Treatment Period

The SCD-SAF will assess sickle cell-related symptoms, including an assessment of pain on an 11-point numerical rating scale (NRS) (0 [no symptom] to 10 [worst possible symptom]), using a daily eDiary by participants. Depending on the version of SCD-SAF used by the participant, 7 questions (Version 1) or 8 questions (Version 2) about the symptoms over the past 24 hours are asked, including the worst pain, the worst fatigue, the worst swelling, the worst numbness, the worst tingling (Version 2 only), the worst stiffness, shortness of breath, and difficulty concentrating. If 8-question SCD-SAF (Version 2) is used, SCD-SAF total score is the sum of the 8 sub-scores. If the 7-question SCD-SAF (Version 1) is used, SCD-SAF total score is the sum of the 7 sub-scores multiplied by (8/7). If any individual score is missing, the total score is set as missing. Individual scores include pain sub-score, fatigue sub-score, swelling sub-score, numbness sub-score, tingling sub-score, stiffness sub-score, shortness of breath sub-score, difficulty concentrating sub-score.

The baseline NRS will be determined based on the average of available daily NRS data during the 7 days prior to randomization. The weekly NRS scores are calculated as the average of available daily NRS scores for each week postdose (Week 1 = Day 1 to 7, Week 2 = Day 8 to 14...). The EOT NRS score is the last weekly NRS score collected after the first dosing date and through the last dosing date plus 4 days.

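### The EOT SCD-SAF score can rest on only 1 to 3 diary days after an early EOT visit, although a full week of entries exists

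*SAP*

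**What the plan says.** SAP 8.4.1.1 builds every SCD-SAF score from the daily eDiary. A weekly score is the "average of available daily NRS scores for each week postdose", with blocks fixed from Day 1: "Week 1 = Day 1 to 7, Week 2 = Day 8 to 14", after which the series is left open. For end of treatment: "The EOT NRS score is the last weekly NRS score collected after the first dosing date and through the last dosing date" plus 4 days. Change from baseline in total score at EOT is a listed endpoint (SAP Table 1 and 8.4.1.1), with ANCOVA comparisons against placebo.

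Baseline is the "average of available daily NRS data during the 7 days prior to randomization", also without a minimum. The only day-count rule for the diary is Protocol Inclusion 12 ("Patient completes daily eDiary entries for at least 10 days during the last 14 days of the Run-in Period"), and it governs eligibility, not scoring. SAP 5.3 deals with partial dates, 5.4 with visit mapping, and 6.6 with compliance summaries. None sets a minimum for a diary score.

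On timing, Protocol 3.1 says that the Treatment Period "will end after the End-of-Treatment (EOT) Visit on Day 85 (-7/+4"), that is, on any of Days 78 to 89. At that visit patients "will return their eDiary and any unused study drug". SAP Tables 5a and 5b give the same window and the same eDiary return for Amendment 3 and for Amendments 4 and 5.

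**The concern.** Block boundaries are tied to Day 1, but the diary ends on whatever day the EOT visit is held. The last block is therefore often incomplete, and the rule takes it in place of the full week before it. Diary days that would give a 7-day score exist but are not used, so the precision of the EOT score depends on visit scheduling.

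The open-ended week series adds an ambiguity. The EOT target, Day 85, would be the first day of a Week 13, while the eDiary compliance table (SAP Table 6) stops at Week 12. Two programmers could code EOT differently for a patient seen exactly on target.

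The SAP sets completeness rules elsewhere: a missing item voids the daily total score, ASCQ-Me needs 4 of 5 items, and analgesic days are rescaled for incomplete weeks. For the number of days behind an SCD-SAF score it has no rule.

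**Working it through.** The plan states no figure for the number of days behind an EOT score, so there is nothing to reproduce. The check is a direct count.

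**Inputs**
- Block *w* = Days 7*w* − 6 to 7*w* (SAP 8.4.1.1). Week 11 = Days 71–77, Week 12 = Days 78–84, and Week 13, if formed, = Days 85–91.
- Visit day *v* = 85 − 7 to 85 + 4 = 78 to 89, which is 12 days (Protocol 3.1). The upper end agrees with the 89-day maximum in Protocol 3.3.
- For a completer the last dose is taken in clinic at the EOT visit (Protocol 3.5.4.1, Schedule of Events) and the eDiary is returned there. The limit "through the last dosing date plus 4 days" therefore neither adds nor removes a diary day.
- Complete diary, with the last entry on day *v* or on day *v* − 1. The documents do not say which.

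**Days in the EOT score by visit day (main reading: any block with an entry counts)**

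| Visit day | 78 | 79 | 80 | 81 | 82 | 83 | 84 | 85 | 86 | 87 | 88 | 89 | Under 4 days |
|---|---|---|---|---|---|---|---|---|---|---|---|---|---|
| To Week 12, visit-day entry | 1 | 2 | 3 | 4 | 5 | 6 | 7 | 7 | 7 | 7 | 7 | 7 | 3/12 |
| To Week 12, no visit-day entry | 7 | 1 | 2 | 3 | 4 | 5 | 6 | 7 | 7 | 7 | 7 | 7 | 3/12 |
| With Week 13, visit-day entry | 1 | 2 | 3 | 4 | 5 | 6 | 7 | 1 | 2 | 3 | 4 | 5 | 6/12 |
| With Week 13, no visit-day entry | 7 | 1 | 2 | 3 | 4 | 5 | 6 | 7 | 1 | 2 | 3 | 4 | 6/12 |

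**Stricter reading (the block must end by last dose + 4 days).** Week 12 qualifies when 84 ≤ *v* + 4, so from Day 80. Week 13 qualifies when 91 ≤ *v* + 4, so from Day 87.
- Without Week 13, scores under 4 days occur on Day 80 (visit-day entry) or on Days 80 and 81 (none): 1/12 or 2/12.
- With Week 13, they occur on Days 80 and 87, or on Days 80, 81, 87 and 88: 2/12 or 4/12. No 1-day score remains.

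**Early stoppers.** If the last diary day is the *j*-th day of its block, the score has *j* days, so it is under 4 for *j* = 1, 2, 3: 3 of 7 positions. On the stricter reading, with the last entry on the last dosing day, 7 − *j* ≤ 4 is needed, so only *j* = 3 remains.

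**Size (illustration; the documents give neither the spread of visit days nor any variance component).** Assume visits centred on Day 85 with SD 2 to 3 days, truncated to Days 78–89. Assume variance shares for person *b* = 0.40–0.60, week *p* = 0.15–0.25 and day *w* = 0.25–0.40, summing to 1. With a 7-day baseline, the residual variance of a *k*-day score is

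R(*k*) = *b* + *p* + *w*/*k* − *b*²/(*b* + *p* + *w*/7).

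Example with *b* = 0.5, *p* = 0.2, *w* = 0.3:
- R(7) = 0.743 − 0.337 = 0.406
- R(1) = 1 − 0.337 = 0.663, ratio 1.63
- R(3) = 0.8 − 0.337 = 0.463, ratio 1.14

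Over the assumed ranges, on the main reading:

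| | EOT from under 4 days | Average R(*k*)/R(7) |
|---|---|---|
| Weeks end at 12 | 1.2% to 11.5% of visits | 1.01 to 1.07 |
| Week 13 formed | 40.6% to 51.1% of visits | 1.13 to 1.32 |

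**After the change.** With a window of the 7 days ending at the last entry, the last entry falls on Days 77 to 89 and the window starts on Day 71 or later. All 12 visit days then give 7 days with a complete diary.

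**The case against.** The SAP never says in words that a partial block counts however short it is; that follows from averaging available days with no minimum. The last dose + 4 days limit can fairly be read as applying to the whole block. That reading stands as a possibility. It cuts the counts to 1–2 of 12 and removes 1-day scores, but it does not remove the problem. A reading in which only full weeks qualify would remove it, but averaging available scores points the other way.

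The larger figures need a Week 13, and no passage names one. SAP Table 6 and the dosing tables stop at Week 12, and the named SCD-SAF time points are Weeks 4, 8, 12 and EOT. The only support is the open-ended series in 8.4.1.1. A reader might infer that about half of patients would have an EOT score from 1 to 3 days, or that an on-target visit normally gives a 1-day score. The documents do not support that: without Week 13, a Day 85 visit gives a full 7-day Week 12 score.

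Little depends on this endpoint. It is exploratory, the sample size has no statistical basis, and Week 12, by-week, overall-period and MMRM results cover the same construct. The Week 12 score and the 30% pain response are shortened only by early visits (Days 78–80, or 78–81 if no visit-day entry is made).

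The count also assumes an in-clinic EOT visit. SAP 3.2 allows remote visits from March 2020, so it need not fit every patient. All of this limits the size of the point, not its existence.

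**Conclusion.** The point holds as a minor one. As written, the rule can score EOT from 1 to 3 days of a complete diary and set aside a full week. With weeks ending at Week 12 this happens on 3 of 12 permitted visit days (1–2 of 12 on the stricter reading). If a Week 13 were formed it would be 6 of 12 (2–4 of 12). These fractions give Day 78 the same weight as the target day, so they do not estimate the share of patients affected.

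A reader might also infer bias in the treatment comparison. Nothing in the documents ties the EOT visit day to treatment arm, so what is shown is added noise. On the better-supported reading that noise is small: residual variance is 1–7% above that of a 7-day score, and this rests on the assumed visit spread and variance components. The missing rule and the day counts are certain given the stated readings; the variance figures are illustrative only.

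**What to change.** In SAP 8.4.1.1:
- Define the EOT diary score as the mean of the available daily scores in the 7 calendar days (from Day 1 onward) ending at the last diary entry within last dose + 4 days.
- Keep fixed Weeks 1 to 12 for all by-week, Week 12, response and MMRM analyses.
- State that no Week 13 is formed.
- State that 8.4.1.1 governs diary scores, not the SAP 5.4 windows, where Week 12 runs from Day 65.

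The cost is SAP wording and derivation code; no new data are needed. The downside is that EOT can overlap Weeks 11 and 12. It will also stop being equal to the Week 12 score for most completers: with a complete diary the two coincide only when the last entry is on Day 84. EOT should therefore be reported as a separate endpoint.

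A minimum number of days is optional and should be chosen from blinded data. For example, 4 of 7 applied to baseline would remove every change score for a patient who met the 10-of-14 run-in rule with 7 days in the first week and 10 − 7 = 3 in the last. How a missing Week 12 response enters the CMH analysis is a separate question and not part of this point.

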#### **8.4.1.2. Sensitivity Analysis of SCD-SAF**

In addition, the following sensitivity analyses will be conducted for SCD-SAF total score, individual scores for pain, stiffness and fatigue, and subtotal score of pain + stiffness + fatigue, using ITT Population.

1. Summary using descriptive statistics for participants enrolled under Protocol Amendment 4 or later, with PBO2, and 18 mg olinciguat (split into 6 mg, 12 mg, 18 mg groups based on the last uptitration)
2. MMRM mentioned in [Section 8.3.2](#) will be fitted to estimate the differences in change from baseline/percent change from baseline of scores between each olinciguat group and the specified placebo group for each visit

#### **8.4.2. Adult Sickle Cell Quality of Life Measurement Information System (ASCQ-Me)**

The ASCQ-Me endpoint is the change from baseline in ASCQ-Me subscale scores at Week 1, 4, 8, and 12.

The ASCQ-Me is a study visit questionnaire to assess the physical, social, and mental impact of SCD on adults in the past 7 days, 30 days, or 12 months. The 3 domains of the ASCQ-Me consist of the following subscales: pain impact, pain episodes, sleep impact, and stiffness impact (physical health), emotional impact (mental health), and social functioning impact (social health). Participants will complete all the subscales except the pain episodes subscales. Participants respond using verbal rating scales (eg, Never, Rarely, Sometimes, Often, Always).

For each subscale, there are five items; four out of five items need to be answered in order to compute score. The sub-scales are scored by summing the values for each response and using the conversion tables in [Appendix A](#) to obtain the score [1]. In the case that only 4 out of 5 items were completed, a score can be approximated by first summing up the 4 answered items and then multiplying by 1.25. A higher score represents better self-reported health for the emotional, pain, sleep, social, and stiffness impact domains. For example, a score of 60 on the emotional impact measure is 1 SD higher than the average US general population, indicating better health.

For each ASCQ-Me subscale score, the observed value and the changes from baseline will be summarized by treatment group and visit. In addition, ANCOVA model mentioned in [Section 8.1](#) will be fitted to estimate the difference in change from baseline of subscale score between each olinciguat group and the placebo group, at each visit.

#### **8.4.3. Patient-reported Outcomes Measurement Information System (PROMIS)**

The PROMIS endpoint is the PROMIS fatigue score at Week 1, 4, 8, and 12.

This document is confidential.

The Patient-reported Outcomes Measurement Information System (PROMIS) Fatigue—Short Form 7a is a self-administered questionnaire at study visit that assesses the impact and experience of fatigue in the 7 days prior to the administration of the questionnaire. Participants respond to concepts such as 'Feel Tired', 'Extreme Exhaustion', 'Out of Energy', 'Limit at Work', 'Think Clearly', 'Bath or Shower', and 'Exercise' using a verbal rating scale (eg, Never, Rarely, Sometimes, Often, and Always).

The total raw score can be derived if there are no missing data. All questions must be answered to produce a valid score. The total raw score is derived by summing the values of the response to each question; and then the total raw score will be converted to the PROMIS fatigue score by using the conversion tables in [Appendix B \[2\]](#). A higher PROMIS fatigue represents more of the concept being measured. A PROMIS fatigue of 60 is one SD worse than the average United States general population and a PROMIS fatigue of 40 is one SD better than average.

For PROMIS fatigue score, the observed value and the changes from baseline will be summarized by treatment group and visit. In addition, ANCOVA model mentioned in [Section 8.1](#) will be fitted to estimate the difference in change from baseline of PROMIS fatigue score between each olinciguat group and the placebo group, at each visit.

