5.10.2.5 PROMIS Fatigue Short Form 7a

Descriptive analysis and change from baseline will be computed for the PROMIS Fatigue Short Form 7a by treatment arm. The HealthMeasures scoring service can be used to score the questionnaire using the response pattern scoring method. Alternatively, a total raw score can be derived if there are no missing data. All questions must be answered to produce a valid score. If a question is skipped, the HealthMeasures scoring service should be used to create a final score.

A higher PROMIS T-score represents more of the concept being measured. A T-score of 60 is one SD worse than the average United States (US) general population and a T-score of 40 is one SD better than average.

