## 2. Purpose

This statistical analysis plan (SAP) describes the planned analysis of the safety, tolerability, efficacy and PK data from Study C1701-202, a randomized, placebo-controlled, Phase 2 study to evaluate the safety and pharmacodynamics of once-daily (QD) oral olinciguat (IW-1701) in participants with stable sickle cell disease (SCD). A detailed description of the planned tables, figures, and listings (TFLs) to be presented in the clinical study report (CSR) is provided in the accompanying TFL shell document.

Note: Throughout this SAP, reference to “IW-1701” is replaced by its international nonproprietary name (olinciguat), where possible.

The intent of this document is to provide additional detailed guidance for the planned statistical analyses of the safety, tolerability, efficacy and PK data as defined in the study protocol. Any changes to the protocol planned analyses must be agreed upon between Cycleron [REDACTED] and documented under [Section 11](#) (Changes from Analysis Planned in Protocol).

This SAP must be finalized prior to locking of the clinical database for this study. When the SAP and TFL shells are agreed upon and finalized, they will serve as the template for the analyses presented in this study’s CSR, along with the final version of the protocol, as applicable. This SAP supersedes the statistical considerations identified in the protocol; where considerations are substantially different, they will be so identified. If additional analyses are required to supplement the planned analyses described in this SAP, they may be performed and will be identified in the CSR. Any substantial deviations from this SAP will be agreed upon between Cycleron [REDACTED] and identified in the CSR.

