## 11. Changes from Analysis Planned in Protocol

In Protocol Section 4.2.3 (patient-reported outcomes), both number and proportion of days of work/school missed due to SCD symptoms at Weeks 4, 8, 12 were included.

However, current SAP will summarize and analyze only the number (not proportion) of days of work/school missed due to SCD symptoms at Weeks 4, 8, 12. Since each week has 7 days, the calculated proportion of days of interest doesn't provide additional information.

This document is confidential.

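### SAP 8.4.3 drops, without declaring it, the protocol's fallback scoring for PROMIS Fatigue forms with a skipped item; the resulting loss cannot be sized from the documents

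*SAP*

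**What the plan says.** Protocol 5.10.2.5 offers two scoring routes and a rule for incomplete forms:

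- Route one: "The HealthMeasures scoring service can be used to score the questionnaire using the response pattern scoring method".
- Route two: "Alternatively, a total raw score can be derived if there are no missing data".
- Incomplete forms: "If a question is skipped, the HealthMeasures scoring service should be used to create a final score".

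SAP 8.4.3 retains only route two. It states that "All questions must be answered to produce a valid score" and that "the total raw score will be converted to the PROMIS fatigue score by using the conversion tables in" Appendix B. Neither protocol sentence about scoring through HealthMeasures appears. The only other trace of HealthMeasures in the SAP is the scoring manual in its reference list.

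On changes from the protocol, SAP Section 2 says: "This SAP supersedes the statistical considerations identified in the protocol; where considerations are substantially different, they will be so identified". The same section requires changes to the protocol's planned analyses to be documented in Section 11. Section 11 lists one change: the "current SAP will summarize and analyze only the number (not proportion) of days of work/school missed due to SCD symptoms". PROMIS scoring is not mentioned there.

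**The concern.** The sentence that all questions must be answered stands in both documents. In the protocol it qualifies the raw-sum route, and the next sentence provides for forms that fail it. In the SAP the qualification remains and the provision is gone, so an incomplete form has no route to a score.

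PROMIS fatigue is one form per visit, compared by the visit-wise ANCOVA of SAP 8.1. The MMRM is specified only for Hb and HbF (8.3.2) and for SCD-SAF scores (8.4.1.2). A patient without a score at a visit therefore drops out of that comparison, and no repeated-measures model uses the patient's other visits to compensate. The arms are small, so a few blank items could cost noticeable precision. If blanks were related to the patient's state, the remaining patients would also be a selected group. Answers already collected would go unused although the protocol names a way to score them.

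**Working it through.** The documents state no figure on this point and give no power calculation, so there is nothing to reproduce. The check has a textual part and an illustrative part.

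**Text**

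| Question | Protocol 5.10.2.5 | SAP 8.4.3 |
|---|---|---|
| Complete form | HealthMeasures or raw sum | Raw sum, then Appendix B |
| Form with a skipped item | HealthMeasures | No route given |

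Nothing else in the SAP fills the gap. Section 5.3 on missing data deals with partial or missing dates for events and medications. Section 11 is silent on PROMIS.

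**Illustration (skip rates are assumed)**

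Inputs from the documents:
- Seven items: SAP 8.4.3 names "Feel Tired', 'Extreme Exhaustion', 'Out of Energy', 'Limit at Work', 'Think Clearly', 'Bath or Shower', and 'Exercise", and the Appendix B raw scores run from 7 to 35.
- Approximate arm sizes from SAP 3.4 and 3.5: 40/4 = 10 per arm under Amendment 3 or earlier; 48 × 3/4 = 36 on 18 mg and 48/4 = 12 on PBO2 under Amendment 4 and later.
- Two predose forms, at Run-in and Day 1 (Schedule of Events), with baseline the last non-missing value before dosing (SAP 5.2.1).

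Assumed: each item is skipped with probability p, independently across items and forms.

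- Form unscored under the SAP: f = 1 − (1 − p)^7
- Exactly one item blank: 7p(1 − p)^6
- Both baseline forms unscored: f²
- Change score missing at a visit: 1 − (1 − f)(1 − f²)

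| p | f | One blank | f² | Change missing | Patients missing of 36 / 12 / 10 |
|---|---|---|---|---|---|
| 1% | 6.8% | 6.6% | 0.5% | 7.2% | 2.6 / 0.9 / 0.7 |
| 2% | 13.2% | 12.4% | 1.7% | 14.7% | 5.3 / 1.8 / 1.5 |
| 3% | 19.2% | 17.5% | 3.7% | 22.2% | 8.0 / 2.7 / 2.2 |

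Most affected forms would have a single blank, which is the case the protocol's fallback plainly covers.

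**Effect of clustering.** If a form with any blank has m blanks on average, the share of affected forms is 7p/m. With m = 2 (assumed) this is 3.5%, 7.0% and 10.5% for p = 1%, 2% and 3%, about half of f. If items cannot be left blank, p = 0 and the loss is nil.

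**The case against.** Much of the case on the other side is sound.

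- **Loss is not shown.** A reader might infer that the SAP is losing collected data. The documents do not support that. They give no skip rate and do not say whether a blank is possible. Protocol 3.1 has the Run-in questionnaires completed in an eDiary, and protocol 3.8.9.3 does not state the mode for later visits. The protocol does provide for skipped items, but that does not show that they occur.
- **Baseline.** A reader might suppose that a change score needs two particular complete forms, which under independence would lose 1 − (1 − f)² = 24.6% at p = 2%. With two baseline opportunities the figure is 14.7%. This protection is weaker if the same patients skip the same item every time.
- **Non-random skipping.** Items on work or exercise may seem irrelevant to some patients, but no source in the documents shows that skips follow fatigue or item content. If they did, independence would fail and clustering could reduce the number of affected forms.
- **The protocol rule.** A reader might take response-pattern scoring as required for every form. It is not: the protocol permits it, and equally permits the raw sum for complete forms. Choosing Appendix B for complete forms is no departure.
- **ASCQ-Me.** SAP 8.4.2 prorates when four of five items are answered, which makes the PROMIS rule look odd. But ASCQ-Me is a different instrument with its own manual, and SAP 8.4.1.1 sets the SCD-SAF total to missing when any item is missing. The contrast is not evidence of error.
- **Low stakes.** The primary objective is safety. PROMIS fatigue is exploratory and absent from SAP Table 1, and fatigue is also rated daily in the SCD-SAF, with an MMRM sensitivity analysis.

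These points limit the size and weight of the concern. They do not answer the textual gap. The protocol leaves data-handling details to the SAP, but it specified this one, and SAP Section 2 says departures go in Section 11.

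**Conclusion.** The concern holds as an undeclared omission. A PROMIS Fatigue form with any blank item has a scoring route in the protocol and none in the SAP. The SAP does not literally say that such forms are set to missing; that is the consequence of describing no other route. The affected patient leaves that visit's ANCOVA but not those of other visits.

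The size is unknown. The range of 7% to 19% of post-baseline forms rests wholly on assumed independent per-item skip rates of 1% to 3%; clustering would lower it, and a form that does not allow blanks would make it zero. Baseline is largely protected by the two predose forms. No bias is demonstrated. Because the endpoint is exploratory, this is a cheap improvement and does not threaten the trial's primary conclusions.

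**What to change.** In SAP 8.4.3, restore the protocol sentence so that a form with a skipped item is scored by HealthMeasures response-pattern scoring. Complete forms may keep the Appendix B conversion. State how many answered items are needed before a form is sent for scoring, since the documents do not say. Report by arm and visit how many forms were scored by each method and how many were left unscored.

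If the sponsor prefers complete forms only, declare and justify that in Section 11 and still report the unscored forms.

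The cost is a sentence or two in the SAP, a small external scoring step through a service the protocol already names, and two scoring methods on the same T-score metric. It adds no patient burden. It should be settled before database lock, by which time the SAP must be final.
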